11.2.5. Safety

In case there will be more than 5% of subjects without documented dose for solicited symptoms (i.e., symptom screen not completed), sensitivity analysis will include only vaccinated subjects for doses with documented safety data (i.e., symptom screen completed).

For analysis of solicited, unsolicited adverse events (such as serious adverse events or adverse events by primary MedDRA term) and for the analysis of concomitant medications, all vaccinated subjects will be considered. Subjects who did not report the event or the concomitant medication will be considered as subjects without the event or the concomitant medication respectively.

The following rules will be used for the analysis of solicited symptoms:

- Subject who didn't document the presence or absence of a solicited symptom after one dose will be considered not having that symptom after that dose in the analysis done on "administered dose"
- Subjects who documented the absence of a solicited symptom after one dose will be considered not having that symptom after that dose.
- Subjects who documented the presence of a solicited symptom and fully or partially recorded daily measurement over the solicited period will be included in the summaries at that dose and classified according to their maximum observed daily recording over the solicited period.
- Subjects who documented the presence of a solicited symptom after one dose without having recorded any daily measurement will be considered as having that symptom after that dose (at the lowest intensity).
- Intensity of the following solicited AEs will be assessed as described in [Table 8](#) and [Table 9](#).

Table 8 Intensity scales to be used by the parent(s)/LAR(s) for solicited symptoms during the solicited follow-up period

Adverse Event	Intensity grade	Parameter
Fever*		Record temperature in °C/°F using any age-appropriate route.
Irritability/Fussiness	0	Behavior as usual
	1	Crying more than usual/no effect on normal activity
	2	Crying more than usual/interferes with normal activity
	3	Crying that cannot be comforted/prevents normal activity
Diarrhea\$		Record the number of looser than normal stools/day
Vomiting§		Record the number of vomiting episodes/day
Loss of appetite	0	Appetite as usual
	1	Eating less than usual/no effect on normal activity
	2	Eating less than usual/interferes with normal activity
	3	Not eating at all
Cough/runny nose	0	Normal
	1	Cough/runny nose which is easily tolerated
	2	Cough/runny nose which interferes with daily activity
	3	Cough/runny nose which prevents daily activity

*Fever is defined as temperature $\geq 38.0^{\circ}\text{C}/100.4^{\circ}\text{F}$. The preferred location for measuring temperature in this study will be the oral cavity, the axilla and the rectum.

§ Diarrhea is defined as passage of three or more looser than normal stools within a day.

§ Vomiting is defined as one or more episodes of forceful emptying of partially digested stomach contents ≥ 1 hour after feeding within a day.

Table 9 Intensity scales for diarrhea, vomiting and fever occurring during the solicited period

Adverse Event	Intensity grade	Parameter
Diarrhea \$	0	Normal (0-2 looser than normal stools/day)
	1	3 looser than normal stools/day
	2	4-5 looser than normal stools/day
	3	≥ 6 looser than normal stools/day
Vomiting §	0	Normal (no emesis)
	1	1 episode of vomiting/day
	2	2 episodes of vomiting/day
	3	≥ 3 episodes of vomiting/day
Fever	0	temperature $< 38.0^{\circ}\text{C}/100.4^{\circ}\text{F}$
	1	temperature $\geq 38.0^{\circ}\text{C}/100.4^{\circ}\text{F} - \leq 38.5^{\circ}\text{C}/101.3^{\circ}\text{F}$
	2	temperature $> 38.5^{\circ}\text{C}/101.3^{\circ}\text{F} - \leq 39.5^{\circ}\text{C}/103.1^{\circ}\text{F}$
	3	temperature $> 39.5^{\circ}\text{C}/103.1^{\circ}\text{F}$

\$ Diarrhea is defined as passage of three or more looser than normal stools within a day.

§ Vomiting is defined as one or more episodes of forceful emptying of partially digested stomach contents ≥ 1 hour after feeding within a day.

Note that for all tables described in this section, the way the percentage of subjects will be derived will depend on the event analysed (see table below for details). As a result, the N value will differ from one table to another.

Event	N used for deriving % per subject for Vaccination phase	N used for deriving % per dose for Vaccination phase
Concomitant vaccination	All subjects with study vaccine administered	All study visits with study vaccine administered
Solicited general symptom	Primary analysis: all subjects with study vaccine administered Sensitivity analysis: all subjects with at least one solicited general symptom documented as either present or absent (i.e., symptom screen completed)	Primary analysis: all study visits with study vaccine administered Sensitivity analysis: all study visits with study vaccine administered and with at least one solicited general symptom documented as either present or absent (i.e., symptom screen completed)
Unsolicited symptom	All subjects with study vaccine administered	All study visits with study vaccine administered
Concomitant medication	All subjects with study vaccine administered	All study visits with study vaccine administered

For summaries by MedDRA primary preferred term combining solicited and unsolicited adverse events, solicited adverse events will be coded as per the following MedDRA codes

Solicited symptom	Lower level term code	Corresponding Lower level term decode
Fever	10016558	Fever
Irritability/Fussiness	10022998	Irritability
Diarrhoea	10012727	Diarrhoea
Vomiting	10047700	Vomiting
Loss of appetite	10003028	Appetite lost
Cough/runny nose	10011224	Cough

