5.3. Important protocol deviation not leading to elimination from per-protocol analysis set

Important protocol deviations not leading to elimination from PPS for immunogenicity will be reported by groups. This includes but is not limited to

- Forced randomization: In case of supplies shortage for the next assigned vaccine according to the randomization schedule at the clinical site, the randomization system will use the forced randomization procedure in order to continue to enrol and vaccinate subjects. The system moves seamlessly to the next treatment/randomization number for which vaccine supplies are available. The site will not be aware of the forced randomization event.
- Manual randomization: In case the randomization system is unavailable, the investigator has the option to perform randomization by selecting supplies available at the site according to a pre-defined rule.
- Short follow-up: subjects who completed the last study contact before the minimum length of follow-up requirement (180 days).
- HRV vaccination without documentation of solicited symptoms i.e. for a HRV vaccine dose administered, at least one solicited symptom is not documented as being present or absent.

The full list of reportable protocol deviations is available in the study protocol deviation management plan.

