6.4.2. Additional considerations

Safety analysis will be done per administered dose. Subjects who missed reporting symptoms (solicited/unsolicited or concomitant medications) will be treated as subjects without symptoms (solicited/unsolicited or concomitant medications, respectively). A sensitivity analysis will be performed on documented doses i.e. accounting only for doses where solicited symptoms are indicated as being absent/present in case more than 5% of the doses are not documented.

AE relationship to vaccination is defined as the relationship to at least one study vaccine as identified by the investigator. In case the related vaccine has not been specified the adverse event will be considered related to all study vaccines. The percentage of subjects reporting of causally related solicited symptoms and unsolicited adverse events within the 31-day (Days 1-31) post-vaccination period will be provided by group for each study vaccine separately.

The planned analysis of the percentage of doses and of subjects reporting at least one grade 3 causally related symptom (solicited or unsolicited) during the 8 day (Day 1-Day 8) solicited follow-up period post-vaccination will not be generated considering this analysis is of limited clinical relevance and is not part of the standard analyses planned in other PCV free Rota studies.

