11.2.6. Management of missing data

Demography:

- For a given subject and a given demographic variable, missing measurements will not be replaced.

Immunogenicity:

- For a given subject and a given immunogenicity measurement time point, missing or non-evaluable measurements will not be replaced.

Reactogenicity and safety:

- Subjects who missed reporting symptoms (solicited/unsolicited or concomitant medications) will be treated as subjects without symptoms (solicited/unsolicited or concomitant medications, respectively).

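### The documented-dose sensitivity analysis still counts two gaps in the solicited-symptom data as absent: the undocumented dose of a one-card infant (per subject) and a blank item on a returned card (both rates)

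*SAP*

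**What the plan says.** In the main analysis of solicited symptoms every vaccinated infant counts. SAP 11.2.6 states the missing-data rule without restriction: "Subjects who missed reporting symptoms (solicited/unsolicited or concomitant medications) will be treated as subjects without symptoms". SAP 6.4.2 repeats it.

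SAP 6.4.2 then adds a sensitivity analysis, "accounting only for doses where solicited symptoms are indicated as being absent/present in case more than 5% of the doses are not documented". SAP 11.2.5 describes it in similar terms: "sensitivity analysis will include only vaccinated subjects for doses with documented safety data (i.e., symptom screen completed".

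The denominators are fixed in the table in SAP 11.2.5. Per subject: "Sensitivity analysis: all subjects with at least one solicited general symptom documented as either present or absent (i.e., symptom screen completed". Per dose: "all study visits with study vaccine administered and with at least one solicited general symptom documented as either present or absent". The table gives one row for solicited general symptoms as a class, with no separate N for each symptom. Protocol 8.1.3.1 (Table 11) lists six: fever, irritability/fussiness, diarrhea, vomiting, loss of appetite, and cough/runny nose.

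Among its rules for solicited symptoms, SAP 11.2.5 says that an undocumented symptom is taken as absent, but only for the analysis on administered doses. It gives no rule for a blank symptom inside a dose that the sensitivity analysis keeps.

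SAP 5.3 flags as an important deviation an HRV dose for which "at least one solicited symptom is not documented as being present or absent".

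**The concern.** The sensitivity analysis exists to show whether scoring missing diary data as symptom-free has lowered the reactogenicity rates. It can show this only where the undocumented data leave the denominator. Under the 11.2.5 table some of them stay in.

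- **Per subject.** Cards are handed out at Visits 1 and 2 and returned at Visits 2 and 3 (Protocol 5.5, Table 4), so one can be lost without the other. An infant with a Dose 1 card and no Dose 2 card is in N. The missing dose adds nothing to n, exactly as in the main analysis.
- **Per item.** A dose with one symptom recorded and another blank is in N for both symptoms and cannot be in n for the blank one.

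For these two patterns the sensitivity figure repeats the assumption it is meant to relax. A report that cited agreement of the overall per-subject rates as evidence of robustness would overstate what had been checked. Reactogenicity is a secondary objective.

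**Working it through.** The documents give no expected symptom rate or card-loss rate for this trial, so there is no planned figure to reproduce. Every rate below is an assumption, and missingness is taken as unrelated to symptoms.

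**1. One card of two missing.** Let p be the per-dose symptom rate, ρ the within-infant correlation, and m the share of infants lacking only the Dose 2 card. All infants receive two HRV doses and all have the Dose 1 card.

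- Per-subject rate with full documentation: R = 2p − p² − ρp(1−p). With p = 0.25 and ρ = 0: 0.50 − 0.0625 = 43.8%.
- Main analysis: (1−m)R + mp.
- Sensitivity analysis as written: every infant has a documented symptom after Dose 1, so N and n are unchanged and the rate is again (1−m)R + mp.
- Dose 2 rate: main (1−m)p; sensitivity (1−m)p/(1−m) = p.

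| m | Undocumented share of HRV doses (m/2) | Per subject, main and sensitivity | Per subject, full documentation | Dose 2, main | Dose 2, sensitivity |
|---|---|---|---|---|---|
| 5% | 2.5% | 42.8% | 43.8% | 23.75% | 25.0% |
| 10% | 5% | 41.9% | 43.8% | 22.5% | 25.0% |
| 20% | 10% | 40.0% | 43.8% | 20.0% | 25.0% |

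For m = 10%: 0.90 × 0.4375 + 0.10 × 0.25 = 0.41875. With ρ = 0.3, R = 0.4375 − 0.3 × 0.1875 = 38.1%, and both analyses give 0.90 × 0.38125 + 0.025 = 36.8%.

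The 10% row sits exactly at the 6.4.2 trigger if that is counted over HRV doses; the 20% row is clearly beyond it. SAP 11.2.5 words the trigger by subject: "In case there will be more than 5% of subjects without documented dose for solicited symptoms". That difference is a separate matter.

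This limb does not depend on how the missing-data rule is read. Dropping an undocumented dose while keeping the infant gives the same at-least-once count as scoring that dose symptom-free.

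**2. Blank items.** Let w be the share of doses wholly blank and m the share partly completed with this symptom missing. Missing is scored absent.

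- Main: p(1−w−m).
- Sensitivity as written: p(1−w−m)/(1−w).
- Symptom-specific N: p.

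With p = 20% and w = 6%:

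| m | Main | Sensitivity as written | Symptom-specific N | Share of understatement corrected |
|---|---|---|---|---|
| 0 | 18.8% | 20.0% | 20.0% | 100% |
| 1% | 18.6% | 19.8% | 20.0% | 85% |
| 5% | 17.8% | 18.9% | 20.0% | 52% |
| 10% | 16.8% | 17.9% | 20.0% | 33% |

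The last column is (sensitivity − main)/(p − main) and does not depend on p. With w = 0 the two analyses coincide: at m = 10% both give 18.0%.

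**3. Choice of per-subject rule.** In the 10% row of step 1, three rules can be compared:

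- As written: 41.9%.
- Keep one-card infants only if they have a recorded event: 0.41875/(0.90 + 0.10 × 0.25) = 45.3%, too high.
- Keep only infants documented after every dose received: (0.90 × 0.4375)/0.90 = 43.8%.

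**The case against.** The best defence is that the check is aimed at doses whose symptom screen was not filled in, and it removes those. In the lost-card example it moves the Dose 2 rate from 22.5% to 25.0%. With Dose 2 card loss of 5% in one arm and 20% in the other, the main Dose 2 rates are 23.75% and 20.0%, and the sensitivity rates are 25.0% in both. The secondary endpoint in SAP 4.2 is defined after each dose, and the mock tables report by dose. This stands. A reader might infer that the analysis cannot show what it is meant to test, or that an artificial difference between arms passes through it untouched. The documents do not support that for the per-dose rates. It is true only of the overall per-subject rate (42.8% against 40.0% in both analyses in that example) and of blank items.

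The item-level limb is partly inference. SAP 11.2.5 limits its explicit missing-equals-absent rule to the administered-dose analysis, and its gloss points to screens completed as a whole. If screens are all-or-nothing, nothing is lost. Staff also verify returned cards and chase unreturned ones (Protocol 5.6.13). These points limit the likely size. Against them, SAP 5.3 foresees doses with a single symptom missing, and a common N leaves a blank item nowhere to go but the symptom-free count.

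A reader might also take SAP 5.3 and 11.2.5 as contradictory. They serve different purposes: 5.3 is a deviation flag and does not feed the denominator. Template 17 would show card return by dose and group.

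Finally, requiring documentation after every dose discards events already seen in one-card infants. That is a real cost, but keeping only the known positives biases the rate upward, as step 3 shows.

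**Conclusion.** The concern holds in a limited form. The sensitivity analysis deals with wholly undocumented doses in the per-dose rates and with infants who have no documentation in the per-subject rates. It leaves one-card infants in the overall per-subject rate, and blank items in both rates, effectively counted as absent. That is not what 6.4.2 describes, namely "accounting only for doses where solicited symptoms are indicated as being absent/present".

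In the illustrations the uncorrected understatement per subject is 1.9 points at 10% one-card loss and 3.8 points at 20%. For blank items it is 1.1 points when 5% of doses lack the item and 6% are wholly blank. These sizes rest on assumed rates, independent doses and missingness unrelated to symptoms.

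The analysis runs only above a 5% trigger, safety results are descriptive, and no confirmatory conclusion depends on it. Severity is minor: a cheap improvement.

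**What to change.** In the SAP 11.2.5 table, make the sensitivity denominators symptom-specific:

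- **Per dose:** HRV doses for which that symptom is documented as present or as absent.
- **Per subject:** infants with that symptom documented after every HRV dose they received. Report alongside the number of infants with only one of two doses documented, and their recorded events.

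State in SAP 6.4.2 that the same item-level meaning of documented applies. SAP 5.3 can keep its broader deviation flag.

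The cost is a change of wording and a few lines of programming. N will vary by symptom and be slightly smaller. The per-subject sensitivity rate will also set aside some observed events: in the 10% example, 0.10 × 0.25 = 2.5% of infants have a recorded event that moves to the side display. The main analysis is unchanged.

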11.2.6. Management of missing data

Demography:

- For a given subject and a given demographic variable, missing measurements will not be replaced.

Immunogenicity:

- For a given subject and a given immunogenicity measurement time point, missing or non-evaluable measurements will not be replaced.

Reactogenicity and safety:

- Subjects who missed reporting symptoms (solicited/unsolicited or concomitant medications) will be treated as subjects without symptoms (solicited/unsolicited or concomitant medications, respectively).

11.2.7. Number of decimals displayed

The following decimal description from the decision rules will be used for the demography, immunogenicity and safety/reactogenicity.

Display Table	Parameters	Number of decimal digits
All summaries	% of count, including LL & UL of CI	1
All summaries	% of difference, including LL & UL of CI	2
Demographic characteristics	Mean, median age, SD (age)	1
Reactogenicity	Mean, Min, Q1, Median, Q3, Max for duration	1
Immunogenicity	Ratio of GMT/GMC	2
Immunogenicity	GMT/GMC except Strepto	1
Immunogenicity	GMT/GMC for Strepto	2
Seroresponse	P-value	4

12. ANNEX 2: SUMMARY ON ELIMINATION CODES

Refer to section [5.2](#)

		from 10 to 17 weeks	from 0 to 0 days	from 30 to 48 days	from 21 to 48 days	from 30 to 48 days	from 21 to 48 days
HRV LIQ	N	300	300	300	300	291	291
	n	1	1	8	7	4	4
	%	0.3	0.3	2.7	2.3	1.4	1.4
	range	9 to 17	0 to 9	27 to 76	27 to 76	30 to 56	30 to 56
HRV LYO	N	300	300	299	299	289	289
	n	0	2	4	4	5	3
	%	0.0	0.7	1.3	1.3	1.7	1.0
	range	10 to 16	0 to 3	30 to 61	30 to 61	28 to 61	28 to 61

HRV LIQ = HRV vaccine liquid formulation Lot A

HRV LIQ = HRV vaccine liquid formulation Lot B

HRV LIQ = HRV vaccine liquid formulation Lot C

HRV LYO = HRV vaccine HRV Lyophilised formulation

PRE = pre-vaccination

PII (M2) = blood sample taken one month after Dose 2 of the HRV vaccine (Visit 3)

Adapted = interval used for defining the ATP cohorts for immunogenicity

N = total number of subjects with available results

n/% = number / percentage of subjects with results outside of the interval

range = minimum-maximum for age and intervals

Template 6 Summary of demographic characteristics (Per Protocol Analysis Set of Immunogenicity)

		HRV LIQ N = 244		HRV LYO N = 252		Total N = 998	
Characteristics	Parameters or Categories	Value or n	%	Value or n	%	Value or n	%
Age at Dose 1 of HRV vaccine (weeks)	Mean	11.5	-	11.6	-	11.6	-
	SD	1.19	-	1.20	-	1.22	-
	Median	11.0	-	11.0	-	11.0	-
	Minimum	10	-	10	-	10	-
	Maximum	15	-	16	-	17	-
Age at Dose 2 of HRV vaccine (weeks)	Mean	16.5	-	16.7	-	16.6	-
	SD	1.37	-	1.34	-	1.40	-
	Median	16.0	-	17.0	-	17.0	-
	Minimum	14	-	14	-	14	-
	Maximum	20	-	21	-	22	-
Gender	Female	120	49.2	120	47.6	483	48.4
	Male	124	50.8	132	52.4	515	51.6
Ethnicity	American Hispanic or Latino	1	0.4	0	0.0	3	0.3
	Not American Hispanic or Latino	243	99.6	252	100.0	995	99.7
Race	African heritage / African American	1	0.4	0	0.0	2	0.2
	American Indian or Alaskan native	0	0.0	0	0.0	0	0.0
	Asian - central/south Asian heritage	0	0.0	0	0.0	0	0.0
	Asian - east Asian heritage	0	0.0	0	0.0	0	0.0
	Asian - Japanese heritage	0	0.0	0	0.0	0	0.0
	Asian - south east Asian heritage	0	0.0	0	0.0	0	0.0
	Native Hawaiian or other pacific islander	0	0.0	0	0.0	0	0.0
	White - Arabic / north African heritage	2	0.8	0	0.0	2	0.2
	White - Caucasian / European heritage	240	98.4	247	98.0	984	98.6
	Other	1	0.4	5	2.0	10	1.0
Height at Visit 1 (cm)	Mean	60.7	-	60.6	-	60.5	-
	SD	2.32	-	2.22	-	2.32	-
	Median	61.0	-	61.0	-	61.0	-
	Unknown	2	-	0	-	3	-
Weight at Visit 1 (kg)	Mean	6.2	-	6.1	-	6.1	-
	SD	0.77	-	0.75	-	0.76	-
	Median	6.2	-	6.1	-	6.1	-
BMI at Visit 1 (kg/m²)	Mean	16.7	-	16.7	-	16.6	-
	SD	1.46	-	1.46	-	1.47	-
	Median	16.5	-	16.7	-	16.5	-
	Unknown	2	-	0	-	3	-

HRV LIQ = HRV vaccine liquid formulation Lot A

HRV LIQ = HRV vaccine liquid formulation Lot B

HRV LIQ = HRV vaccine liquid formulation Lot C

HRV LYO = HRV vaccine HRV Lyophilised formulation

N = total number of subjects

n (%) = number / percentage of subjects in a given category

Value = value of the considered parameter

SD = standard deviation

Template 7 Summary of no co-administered vaccination by dose - Exposed Set

Dose1	HRV LIQ N = 300		HRV LYO N = 300		Total N = 1200	
Characteristics	Value or n	%	Value or n	%	Value or n	%
Any	299	99.7	300	100	1199	99.9
Infanrix hexa	299	99.7	300	100	1199	99.9
Dose 2	HRV LIQ N = 300		HRV LYO N = 299		Total N = 1197	
Characteristics	Value or n	%	Value or n	%	Value or n	%
Any	298	99.3	299	100	1195	99.8
Infanrix hexa	298	99.3	299	100	1195	99.8

HRV LIQ = HRV vaccine liquid formulation Lot A

HRV LIQ = HRV vaccine liquid formulation Lot B

HRV LIQ = HRV vaccine liquid formulation Lot C

HRV LYO = HRV vaccine HRV Lyophilised formulation

N = total number of subjects having received the considered dose of HRV

n/% = number/percentage of subjects who received the specified vaccination on the same day as the considered dose of HRV vaccine

Template 8 Summary of vaccinations other than Study vaccines administered from birth until Visit 3, excluding vaccination given on the day of HRV doses - Exposed Set

Before Dose 1	HRV LYO N = 300			Total N = 1200		
Characteristics	#	n	%	#	n	%
Any	25	25	8.3	67	67	5.6
BCG	25	25	8.3	66	66	5.5
Infanrix hexa™	0	0	0.0	1	1	0.1
Between Dose 1 and Dose 2§	HRV LYO N = 300			Total N = 1200		
Characteristics	#	n	%	#	n	%
Any	0	0	0.0	2	1	0.1
Infanrix hexa™	0	0	0.0	2	1	0.1
Between Dose 2 and Visit 3*	HRV LYO N = 299			Total N = 1197		
Characteristics	#	n	%	#	n	%
Any	290	290	97.0	1163	1162	97.1
DTPa+IPV+Hib	0	0	0.0	1	1	0.1
Infanrix hexa™	290	290	97.0	1162	1161	97.0

HRV LIQ = HRV vaccine liquid formulation Lot A

HRV LIQ = HRV vaccine liquid formulation Lot B

HRV LIQ = HRV vaccine liquid formulation Lot C

HRV LYO = HRV vaccine HRV Lyophilised formulation

N = Before Dose 1 and between Dose 1 and Dose 2: total number of subjects having received dose 1 of HRV

Between Dose 2 and visit 3: total number of subjects having received dose 2 of HRV

#= number of doses administered of the specified vaccination excluding vaccination given on the day of HRV doses

n/% = number/percentage of subjects who received at least one specified vaccination between the considered visits
excluding vaccination given on the day of HRV doses

§= up to last contact of conclusion at Visit 3 if dose 2 of HRV was not administered

*= up to last contact of conclusion at Visit 3 if visit 3 was not done

Template 9 Study population (Exposed Set)

		<Each group> N=XXXX	Total N=XXXX
Number of subjects			
Planned, N		xxx	xxx
Randomised, N <cohort name>		xxx	xxx
Completed, n (%)		xxx (xx.x)	xxx (xx.x)
<Unknown>		xxx	xxx
Demographics			
N <cohort name>		xxx	xxx
Females:Males		xxx:xxx	xxx:xxx
Mean Age, <unit> (SD)		xxx.x (xxx.x)	xxx.x (xxx.x)
Median Age, <unit> (minimum, maximum)		xxx (xxx,xxx)	xxx (xxx,xxx)
<MOST FREQUENT CATEGORY OF RACE>		xxx (xx.x)	xxx (xx.x)
<SECOND MOST FREQUENT CATEGORY OF RACE>		xxx (xx.x)	xxx (xx.x)
<THIRD MOST FREQUENT CATEGORY OF RACE>		xxx (xx.x)	xxx (xx.x)

Short group label = long group label

Template 10 Difference in seropositivity/seroprotection rates for Anti- (Each antigen) antibody one month after dose 3 of routine childhood vaccination (Visit 6) between HRV Coadministration group and HRV separate administration group - ATP cohort for immunogenicity

Group	N	%	Group	N	%	Difference in seropositivity (seroprotection) rate			
						Anti- (Each antigen) (cut-off: unit)			
						Groups		Value %	95% CI
HRV_COA			HRV_SEP			HRV_COA minus HRV_SEP			

Notes:

N = number of subjects with available results

% = percentage of subjects who are seropositive (seroprotected) one month after Dose 3 of childhood routine vaccination (Visit 6)

95%CI = asymptotic standardised 95% confidence interval; LL = lower limit; UL = upper limit

Template 11 Ratio of anti-rotavirus IgA antibody GMCs at one month after Dose 2 of the HRV vaccine between each pair of the three lots of the HRV vaccine liquid formulation – Per Protocol Analysis Set of Immunogenicity

Group	N	GMC	Group	N	GMC	GMC ratio		95% CI	
						Ratio order	Value	LL	UL
HRV LIQ	242	384.4	HRV LIQ	260	418.8	HRV LIQ /HRV LIQ	0.92	0.67*	1.26*

HRV LIQ = HRV vaccine liquid formulation Lot A HRV LIQ = HRV vaccine liquid formulation Lot B

HRV LIQ = HRV vaccine liquid formulation Lot C

N = number of subjects with available results

95% CI = 95% Confidence Interval (one-way ANOVA model with pooled variance from the four groups)

L.L. = Lower Limit, U.L. = Upper Limit

*The two-sided 95% CIs are within [0.5; 2] (the pre-defined clinical limit interval for consistency)

